2. SAMPLE SIZE

We aim to recruit 100 households in the intervention group. Similarly, for the comparison group (Control Arm) we will conduct the study in three UCs: Kot Mehdi Shah, Balouqi Wali, and Ameen Garh, and recruit 100 households in the comparison group-Based on power calculations 100 households in each of the groups will allow us to detect a meaningful difference in child weight gain (≥ 400 grams) with 80% power. To address potential attrition, we are building in a 20% buffer.

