October
2025

Women Supporting Women Using Local Solutions to Improve Infant and Young Child Feeding and Care Practices in Punjab, Pakistan

STUDY PROTOCOL

Study Overview

JUSTIFICATION.

This study responds to a call by the Pakistani government and public health researchers who have identified combatting child malnutrition as a high priority for Rahim Yar Khan (RYK) district in the province of Punjab. This study will focus on the proximal causes of malnutrition (inadequate diet and infections).

GOAL.

To rehabilitate moderately malnourished children 7-23 months of age and enable mothers to sustain this healthy growth at home by changing their infant and young child feeding (IYCF), care, hygiene, and health-seeking behaviors.

PURPOSE.

The OVERALL STUDY PURPOSE is to develop and evaluate a behavior change educational program to prevent malnutrition in the province of Punjab, Pakistan. The study has two main phases: the Formative Research Phase and the Intervention Phase.

The PURPOSE OF THE FORMATIVE RESEARCH is to identify uncommon but successful (i.e. *Positive Deviant*) IYCF behaviors practiced by local mothers of well-nourished children from economically disadvantaged homes, and to develop an education program informed by these best-practices and WHO guidelines.

The PURPOSE OF THE INTERVENTION PHASE is to deliver the educational program to mothers with undernourished children in the Intervention arm of the study who are equally disadvantaged, and to evaluate its impact on the growth of children.

STUDY HYPOTHESIS.

The primary hypothesis is that a higher proportion of Index children in the intervention compared to the control group will experience an average weight gain of 400g/month in the first 4 mos of the intervention.

STUDY OBJECTIVES.

1. Understand local perceptions, experiences, and cultural norms around IYCF practices and care,
2. Discover demonstrably successful IYCF behaviours and strategies using local resources,
3. Develop and implement a culturally appropriate and context-specific intervention,
4. Evaluate the intervention using two comparisons: (a) Within the intervention group: assess Index children's growth patterns and change in household behaviours/factors relevant to IYCF (e.g., knowledge, practice, beliefs and norms). (b) Intervention vs control group: compare average weight gain of Index children and household behaviours/factors relevant to IYCF (e.g., knowledge, practice, beliefs and norms)

Research Methods

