1. SETTING

The intervention will be conducted in three Union Councils (UCs): Wah Kohna, 139/P, and Rahim Yar Khan Deh. These UCs were purposively selected based on population need and prior engagement during the formative phase. Our recruitment strategy is progressive: we will maximize recruitment from 1 UC first and only move to the next UC when we have maximized recruitment of households from that UC.

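### The 80% power behind 100 households per arm is not supported for a three-versus-three Union Council design and is not tied to the primary endpoint

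*Protocol*

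**What the plan says.** Protocol, Recruitment Methods, 2. SAMPLE SIZE, sets 100 households per arm and gives one justification: "100 households in each of the groups will allow us to detect a meaningful difference in child weight gain (≥ 400 grams) with 80% power". The one allowance it adds is for losses: "To address potential attrition, we are building in a 20% buffer".

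The layout is in the same part of the protocol. Under 1. SETTING the intervention goes to three UCs, of which it says: "These UCs were purposively selected based on population need and prior engagement during the formative phase". They are filled in sequence: "we will maximize recruitment from 1 UC first and only move to the next UC". Under 2. SAMPLE SIZE, "for the comparison group (Control Arm) we will conduct the study in three UCs", and the three named there are different from the intervention UCs. A household's arm is thus decided by the UC it lives in.

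The primary hypothesis, under STUDY HYPOTHESIS in the Study Overview, is that "a higher proportion of Index children in the intervention compared to the control group will experience an average weight gain of 400g/month", assessed over the first 4 months of the intervention.

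**The concern.** There are two separate gaps between the power statement and the trial it is meant to justify.

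- **Layout.** With arm fixed by UC, children in one UC share health workers, facilities and local conditions, so their outcomes may be correlated. The between-arm contrast then rests on six UCs, with at most 4 between-UC degrees of freedom. The sample-size section mentions neither point.
- **Endpoint.** In the hypothesis, 400 g/month is a threshold that each child does or does not reach, averaged over 4 months, and the arms are compared on a proportion. In the sample-size section, 400 g is worded as a detectable difference in weight gain, with no period and no response proportions.

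The 80% is the only support for 100 per arm. As it stands, a reader cannot tell what difference in the primary proportion, or in mean gain, this design can detect.

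**Working it through.** **Inputs from the protocol:** 100 households per arm, 80% power, 400 g, 20% buffer, three UCs per arm (1. SETTING and 2. SAMPLE SIZE); threshold of 400 g/month over 4 months (STUDY HYPOTHESIS).

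**Assumptions, none stated in the protocol:** two-sided 5%; ICC 0.01, 0.02 and 0.05; the SDs and response proportions below; 100 analysed per arm and equal UCs unless noted.

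**1. The plan's own figure.** It cannot be reproduced without an SD and alpha. Solving backwards, a two-sample t-test at 100 per arm has 80% power at a standardised difference of d = 0.398. For 400 g this means SD = 400/0.398, about 1,005 g.

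**2. Design effect.** DE = 1 + (100/3 − 1) × ICC, which is 1.32, 1.65 and 2.62 at ICC 0.01, 0.02 and 0.05.

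**3. Mean difference of 400 g.** The noncentrality is (400/SD) × √(100/(2 × DE)). Power is Φ(noncentrality − 1.96), or the noncentral t on 2 × (3 − 1) = 4 df. Example at SD 1,005 g and ICC 0.02: 0.398 × √(100/(2 × 1.647)) = 2.19, and Φ(0.23) = 59%.

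| SD | Normal approximation, ICC 0.01/0.02/0.05 | 4 df, ICC 0.01/0.02/0.05 |
|---|---|---|
| 1,005 g | 69/59/41% | 46/39/27% |
| 800 g | 87/79/59% | 64/55/39% |
| 600 g | 98/96/83% | 86/78/60% |
| 400 g | at least 99% | 99/98/90% |

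At SD 1,005 g, power on 4 df is 57% even with ICC 0, so few UCs cost power apart from any correlation.

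**4. Responder proportion (the primary endpoint).** The noncentrality is (p2 − p1)/√(DE × [p1(1 − p1) + p2(1 − p2)]/100).

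- 30% vs 49%, no clustering: 0.19/√(0.4599/100) = 2.80, which gives 80%. With clustering: 68/59/41% (4 df: 46/39/27%).
- 30% vs 60%, with clustering: 97/94/79% (4 df: 82/74/55%).
- Intervention proportion needed for 80% power when control is 30%: 49% without clustering, and 52/54/60% with it. On 4 df it is 55% at ICC 0 and 59/62/70% with clustering.

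**5. Two further unknowns, at SD 1,005 g, normal approximation.**

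- If the buffer sits inside the 100, 100 × 0.80 = 80 are analysed. DE is 1.26/1.51/2.28 and power is 61.3/53.5/38.5%.
- If sequential filling gives 60/30/10 in the intervention arm, the size-weighted mean UC size is (60² + 30² + 10²)/100 = 46. DE in that arm is 1 + 45 × ICC. With control UCs equal, power is 67/56/38%.

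**The case against.** The strongest reply has four parts.

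- **The SAP may hold the inputs.** The protocol refers to power calculations that are not shown, and an SD, alpha or ICC may reasonably sit in the SAP. This stands as far as it goes: missing inputs alone are not the finding, and silence does not prove that clustering was ignored. But the layout and the mismatch of endpoint are both in the protocol, and an unseen SAP does not reconcile them.
- **A mean-gain target has a home.** STUDY OBJECTIVES, 4(b), plans a between-arm comparison of average weight gain, and the greater-or-equal sign may be shorthand for a responder threshold. Both readings are fair. The first ties the 80% to an objective but not to the primary hypothesis. The second still lacks the 4-month average and both proportions.
- **The large losses come from a back-solved SD.** This is correct. Nothing in the protocol supports 1,005 g, which is 2.5 times the stated difference. The 4 df analysis is also not one the protocol specifies. The losses are therefore conditional, and the smaller-SD rows matter as much as the first.
- **It is partly a feasibility study.** 5. CONSENT PROCESS says so. Even so, the protocol states a comparative primary hypothesis and claims formal power for it.

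**Conclusion.** The concern holds: the 80% is unsupported for three versus three UCs and is not linked to the primary endpoint. It does not follow that power is below 80%. Under the assumptions above, the loss runs from negligible (SD 400 g) to large (41% by normal approximation, 27% on 4 df, at SD 1,005 g and ICC 0.05). If a household-level calculation was only just met at 100 per arm, the stated figure overstates power. If the true effect is large relative to its variability, power may still be adequate. Only a restated calculation can settle which. This should be fixed, since it is the sole basis for the sample size.

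**What to change.** Rewrite the power statement in 2. SAMPLE SIZE, as power or as a detectable difference, so that it does the following:

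- addresses the primary endpoint (proportion averaging 400 g/month over the first 4 months), with assumed control and intervention proportions;
- if a 400 g mean difference is also intended, gives it separately, with its SD and period;
- states alpha and a range of ICCs, and covers UC sizes from equal to clearly unequal, given the sequential filling;
- says whether the 100 is before or after the 20% buffer;
- rests on a between-arm comparison that accounts for UC, with degrees of freedom suited to six UCs;
- acknowledges that this does not remove the confounding of arm with purposively chosen UCs.

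The cost is one recalculation and a rewritten paragraph. The stated power will probably look less favourable. No extra households are requested and recruitment does not change.

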Anthropometric Assessment. Each Index Child's weight and height will be measured at the start and end of each hearth session, and at the end of the 2-week home visits (Day 1, Day 13, Day 27 of each cycle). If, by the end of the cycle, the child has not gained at least 400g, they will be invited to repeat the cycle—up to a maximum of three cycles. Children failing to any gain weight between cycles will be referred to a public health facility for medical evaluation. Z-Scores will be calculated to quantify the child's nutritional status. Mid-Upper Arm Circumference (MUAC) will be taken to assess for wasting. During the follow-up period, the child's weight will be monitored monthly for up to six months post-intervention.

Health assessment.

Baseline health assessments will be conducted at local public health facilities within two weeks prior to the first Hearth session for participants in the treatment arm. Each Index Child will receive a full medical examination by a physician, a Hematocrit (Hb) test via finger prick, and verification and updates for routine immunizations.

All children showing "failure to thrive" (e.g., no weight gain or weight loss after a Hearth cycle) will be referred for medical assessment within five days, and accompanied by study staff.

Results of participants' health assessments will not be shared or retained by the research team. This assessment will be conducted solely to confirm that the child meets eligibility criteria and is well enough to participate in the 28-day behaviour change program. This information is sufficient for enrollment purposes, and no medical or health records beyond the anthropometric measurements will be collected, stored, or used as study data

Data collection

Data will be collected using structured tools and include:

Baseline and follow-up household surveys (at 6 months, and possibly 12 months post-intervention if funding permits): surveys will assess 24-hour food recall and indicators on feeding practices, WASH, gender roles, and health-seeking behaviour. Study survey instrument is attached to Section 9.5.

All data will first be recorded on paper and later digitized by trained personnel.

PROCEDURES FOR PARTICIPANTS IN THE CONTROL ARM

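### The sample size section gives 100 households per arm as both the recruitment target and the powered number, yet claims a 20% attrition buffer, and its 400 g effect is not tied to the primary proportion

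*Protocol*

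**What the plan says.** All the figures for the first part are in Protocol, Recruitment Methods, 2. SAMPLE SIZE.

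- Recruitment aim, intervention arm: "We aim to recruit 100 households in the intervention group".
- Recruitment aim for the control arm, followed at once by the number behind the power statement: "recruit 100 households in the comparison group-Based on power calculations 100 households in each of the groups".
- Effect, power and attrition allowance: "difference in child weight gain (≥ 400 grams) with 80% power. To address potential attrition, we are building in a 20% buffer".

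No larger recruitment total and no smaller number for analysis appears anywhere else in the Protocol.

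For the second part, the primary hypothesis (Study Overview, STUDY HYPOTHESIS) is that "a higher proportion of Index children in the intervention compared to the control group will experience an average weight gain of 400g/month", judged over the first four months of the intervention. Objective 4(b) in the same overview also plans, between arms, to "compare average weight gain of Index children". Under Procedures, Anthropometric Assessment for the treatment arm, 400 g is a criterion for one child within one cycle: if "the child has not gained at least 400g, they will be invited to repeat the cycle".

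**The concern.** A buffer for attrition is the gap between the number enrolled and the number the power calculation needs. The section prints 100 for both, so the gap is zero while the text says it is 20%. A reader cannot tell how many analysed children the 80% refers to. Field staff have one printed target, 100. If 100 is the number needed, stopping there builds in a shortfall that is hard to repair once enrolment has closed.

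The second difficulty is what the 80% is for. The section describes a difference in weight gain of at least 400 g and gives no period. The primary hypothesis is a comparison of proportions, with a cut-off of 400 g per month averaged over four months. A difference in mean gain and a difference in responder proportions need different calculations, and the text does not say which one was done.

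**Working it through.** **Inputs from the Protocol.** Recruited: 100 per arm. Number attached to 80% power: 100 per arm. Attrition allowance: 20%. Primary cut-off: an average of 400 g/month over 4 months, so 400 × 4 = 1,600 g per child.

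**Assumptions, not in the Protocol.** Two-sided 5% test, a full 20% loss, independent households.

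**Can the plan's own figure be reproduced?** No. The section gives no significance level, standard deviation or arm proportions. (They may be in an analysis plan that is not shown, so their absence is not the point.) Two readings can be back-solved:

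- *Difference in mean gain of 400 g.* The SD at which 100 per arm gives 80% is 400 / [(1.960 + 0.842) × √(2/100)] ≈ 1,010 g. Smaller SDs would need fewer children: about 16, 36 and 63 per arm at SDs of 400, 600 and 800 g.
- *Difference in responder proportions.* At 100 per arm, 80% power corresponds to pairs such as 10% vs 25%, 30% vs 49.3% or 50% vs about 69%.

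Both readings can be made to fit 100, so the number does not reveal which was used.

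**The buffer.** If N₀ is the number per arm that gives 80%, power at n per arm for the same effect is approximately

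Φ( (1.960 + 0.842) × √(n/N₀) − 1.960 ).

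| Reading | Needed (N₀) | Recruited | Left after 20% loss | Power |
|---|---|---|---|---|
| 100 needed, 100 recruited | 100 | 100 | 100 × 0.8 = 80 | Φ(2.802 × 0.894 − 1.960) = Φ(0.546) ≈ 71% |
| 100 needed, buffer on top as × 1.2 | 100 | 120 | 120 × 0.8 = 96 | Φ(2.802 × 0.980 − 1.960) = Φ(0.785) ≈ 78% |
| 100 needed, buffer on top as ÷ 0.8 | 100 | 125 | 125 × 0.8 = 100 | 80% |
| Buffer inside the 100, as ÷ 0.8 | 80 | 100 | 80 | 80% |
| Buffer inside the 100, as × 1.2 | 100 / 1.2 ≈ 83 | 100 | 80 | Φ(2.802 × √(80/83.3) − 1.960) ≈ 78% |

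The two-proportion formula with pooled variance gives the same 71% and 78% for pairs set to 80% at 100 per arm. That agreement follows from fixing each pair at 80%; it is not separate evidence.

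The first row keeps 100 in both roles and has no buffer. Rows two and three change the recruitment target. Rows four and five change the powered number. No row keeps all three statements.

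**The meaning of 400 g.** Side by side, 400 g is a monthly average for one child in the hypothesis, a gain for one child within a 28-day cycle in the program overview and the treatment-arm assessments, and a difference in weight gain without a period in the sample size section. The last could be the responder cut-off with its period left out, the per-cycle threshold, or a difference in means as in objective 4(b).

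**The case against.** The best defence is that no sum in the section is wrong. Read in order, it gives an aim, then the power at that number, then a separate sentence adding a buffer. The natural intention would be 100 needed with 20% on top and the inflated total simply not printed. That intention is plausible, and the defect may be one of wording. But 100 is the only recruitment figure printed, it is printed for each arm, and it would have to change under that reading. Adding 20% would also give 120, which after a 20% loss leaves 96.

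On the second part, the defence is stronger. A reader might infer that the power was calculated for something other than the primary comparison. The document does not establish that. Elsewhere 400 g is consistently a threshold for one child, and the ≥ sign suits a threshold, so the figure may well be the responder cut-off with its period omitted. What stands is narrower: the text does not show that the 80% applies to the primary proportion.

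A reader might also want to discount the power for clustering, since the arms are drawn from different Union Councils and Hearths run in groups. The Protocol does not support a figure. It gives no intracluster correlation. It fills one Union Council before moving to the next, so an even spread cannot be assumed. Hearth groups exist in the treatment arm only, so one design effect would not fit both arms. Independence is therefore stated here as an assumption and not adjusted for.

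Asking for every input of the calculation would be a request for detail that an analysis plan may hold; it is not part of this point.

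**Conclusion.** The inconsistency is real. As printed, either the recruitment target or the powered number is wrong, and nothing else in the Protocol settles which. The loss of power from 80% to about 71% applies only if 100 is the number needed, enrolment stops at 100 and the full 20% is lost, with a two-sided 5% test and independent households. If the buffer is already inside the 100, the 80% may stand, but at about 80 (or about 83) per arm and not at 100.

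The link between the stated power and the primary hypothesis is not shown; it is not disproved either. A reader might conclude that 100 per arm is too few. That does not follow: the assumed effect and its variability are not given, and under some readings 100 would be more than enough. The point should be fixed, preferably before enrolment closes.

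**What to change.** In Recruitment Methods, 2. SAMPLE SIZE:

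1. State the recruited and the evaluable number per arm separately.
2. Restate the power or the detectable difference at the evaluable number (about 80 per arm if 100 are recruited and 20% are lost).
3. Express that figure for the primary proportion over the first four months or, if 400 g is the responder cut-off, say so and add that it is per month.

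This costs one paragraph, with no new data and no change of endpoint. Stating the numbers correctly requires no extra enrolment. Only if the sponsor wants 100 evaluable per arm after a 20% loss would the target become 100 / 0.8 = 125 per arm, or 2 × 25 = 50 more households in total. The downside is that the stated power or detectable difference may turn out less favourable than the present text suggests.

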3. GATEKEEPERS

Lady Health Workers (LHWs) will act as trusted intermediaries, identifying eligible households and introducing the study to the households. For villages, tibbas, or basties not previously included in the FGDs or PDIs, the research team will collaborate with the CAC and local community leaders to raise awareness about the study. Public announcements and town hall meetings will be organized to inform community members. Interested households will be encouraged to register their names with designated gatekeepers, who will then share this information with the recruitment team.

4. ELIGIBILITY ASSESSMENT

To determine eligibility for participation, each Index Child will undergo a multi-step assessment process.

- Assessment of the child's nutritional status. Only those children identified as being moderately malnourished admitted into the study. Children will be assessed by the field staff through anthropometric measurements: weight, length/height, and mid-upper arm circumference (MUAC) and using standardized WHO growth reference tools. Children will only be included if they are classified as moderately underweight (weight-for-age Z-score between -2 and -3 SD). Severely malnourished children will be referred immediately to a health facility for medical care. All measurements will be conducted by trained staff following strict protocols to ensure consistency and accuracy.

To be eligible for the Treatment Arm. All children meeting the classification of moderate malnutrition will undergo a complete medical at the local health facility, including confirmation of their nutritional status and update of their vaccination record. Eligibility will be determined by working with the Lady Health Worker affiliated with the respective household, who will rule out children with chronic disease according to the exclusion list. A final confirmation from the health facility will be sought after consent is obtained to assess whether the child is well enough to participate in the 28-day behavior change (Hearth) program.

- To be eligible for the Control Arm. All children meeting the classification of moderate malnutrition will be assessed for chronic illness. Initial assessment will be done by asking mothers about their child's health and final eligibility confirmed by Lady Health Workers' medical records.
- Assessment of the household eligibility. Households will undergo an assessment of their wealth ranking and food security status. Study staff will use the Final Recruitment Screening Form to confirm and document eligibility for participation. The recruitment forms for both the treatment and control arms are attached in Section 9.5.

5. CONSENT PROCESS

If the above eligibility criteria are met, on the same day, study staff will discuss the details of the consent process with the household and prepare for the signing of the consent document. The households in the treatment arm will then visit the health facility within one week for medical clearance. One week later, staff will visit the household to collect the signed consent form and conduct the baseline survey. Clearance from the health facility must be obtained before the household begins Hearth sessions. This clearance serves as a second check for exclusion due to disabilities or chronic disease.

To ensure that every participant fully understands the nature of the study before deciding to take part, the informed consent process will be conducted with care, cultural sensitivity, and attention to literacy needs. All consent materials will be provided in Punjabi and Saraiki, the local languages most commonly spoken in the study communities. Trained field staff will visit households in person to explain the study using simple, conversational language. They will walk families through all key aspects of participation, including the purpose and title of the research, the expected duration and structure of the study, what will be asked of them, and what potential risks or benefits may arise.

As this is a community-based study intended to test the feasibility of this intervention in rural Pakistan, the consent process will carefully explain the purpose, procedures, and expectations. This will include what health assessments will be conducted, how data will be collected and stored, and the confidentiality protections in place. Importantly, participants will be reminded that their involvement is entirely voluntary, and they may withdraw at any time without penalty or consequence, as outlined clearly in the consent form. While the study will obtain written

consent at the time of recruitment, on-going verbal consent will be sought at critical junctures to reaffirm willingness to participate. For example, for the Treatment Arm, this will include prior to engaging with hearth cycles 2 and 3 if participants are eligible, and prior to conducting follow-up surveys at 6 and 12 months. At households' request, trusted community members may also be engaged to help explain the protocol and answer questions. Each participating household will receive a printed copy of the consent form for their own records.

As is typical in Pakistan, the mother of the Index Child will be asked to provide consent by signing the form to confirm her understanding and agreement. If the father is available, the father may also provide consent. In households where literacy is limited, participants will be offered the option to give consent using a thumbprint, in keeping with ethical research standards. Refer to Section 9.2 for the consent forms.

Procedures

PROCEDURES FOR PARTICIPANTS IN THE TREATMENT ARM

28-Day Behavior Change Practice Program.

The study's community-based intervention model consists of a 28-day behavior change practice program: groups session in a home-like setting (Heath) where mothers and the moderately malnourished Index Child (and interested family) will come together to learn new ways of cooking and practicing successful behaviours to rehabilitate their malnourished child., followed by home practice. Each 28-day program cycle consists of two components:

1- Group Hearth Sessions (2 weeks in duration): Mothers and their Index Child will attend the hearth in small groups (typically 15 mother-child pairs). Sessions will focus on knowledge about complementary feeding, active feeding, hygiene, caregiving, and health-seeking behaviours. Mothers will take part in cooking and caring demonstrations, rotating through roles to build hands-on skills. Accompanying family members may participate to support learning and adoption of new behaviours.

2- Home Practice (2 weeks in duration): After the group sessions, field staff will visit each home three times per week to support the mother's practice of newly learned behaviors. Each visit will last approximately 1.5 hours and will reinforce positive changes and problem-solve emerging challenges.

Mothers are expected to contribute some items of their choice to the hearth (e.g., food items for 1-2 children: egg, rice, vegetables, or water, or household materials (e.g., utensils for their child: spoon, cup/ bowl, or soap) to the sessions, ensuring that activities reflect real-life constraints and available resources. It is hoped active participation will promote engagement and help transition practices in the home setting. The project will contribute cooking pots, utensils and most of the food for the 2-week home-like sessions.

Assessment

Anthropometric Assessment. Each Index Child's weight and height will be measured at the start and end of each hearth session, and at the end of the 2-week home visits (Day 1, Day 13, Day 27 of each cycle). If, by the end of the cycle, the child has not gained at least 400g, they will be invited to repeat the cycle—up to a maximum of three cycles. Children failing to any gain weight between cycles will be referred to a public health facility for medical evaluation. Z-Scores will be calculated to quantify the child's nutritional status. Mid-Upper Arm Circumference (MUAC) will be taken to assess for wasting. During the follow-up period, the child's weight will be monitored monthly for up to six months post-intervention.

Health assessment.

Baseline health assessments will be conducted at local public health facilities within two weeks prior to the first Hearth session for participants in the treatment arm. Each Index Child will receive a full medical examination by a physician, a Hematocrit (Hb) test via finger prick, and verification and updates for routine immunizations.

All children showing "failure to thrive" (e.g., no weight gain or weight loss after a Hearth cycle) will be referred for medical assessment within five days, and accompanied by study staff.

Results of participants' health assessments will not be shared or retained by the research team. This assessment will be conducted solely to confirm that the child meets eligibility criteria and is well enough to participate in the 28-day behaviour change program. This information is sufficient for enrollment purposes, and no medical or health records beyond the anthropometric measurements will be collected, stored, or used as study data

Data collection

Data will be collected using structured tools and include:

Baseline and follow-up household surveys (at 6 months, and possibly 12 months post-intervention if funding permits): surveys will assess 24-hour food recall and indicators on feeding practices, WASH, gender roles, and health-seeking behaviour. Study survey instrument is attached to Section 9.5.

All data will first be recorded on paper and later digitized by trained personnel.

PROCEDURES FOR PARTICIPANTS IN THE CONTROL ARM

Participants in the control group will be enrolled after staff use the Final Recruitment Screening for Control Form to confirm eligibility, and households that express interest will be invited to join. Unlike the intervention group, control participants will not undergo a health facility-based assessment at baseline, will also not participate in the 28-day behavior change practice program, and will instead continue to receive routine care from LHWs and access health services as usual.

They will participate in the baseline and follow-up household surveys (at 6 months, and possibly 12 months post-intervention if funding permits): surveys will assess 24-hour food recall and indicators on feeding practices, WASH, gender roles, and health-seeking behaviour. Study survey instrument is attached to Section 9.5.

Anthropometric Assessment. Each Index Child's weight and height will be measured at the time of baseline and endline survey. Z-Scores will be calculated to quantify the child's nutritional status. Mid-Upper Arm Circumference (MUAC) will be taken to assess for wasting. During the follow-up period, the child's weight will be monitored monthly for up to six months post-baseline.

Time to Participate

For Treatment arm:

If a household were to partake in one hearth cycle and complete the full 6-month participation we will be offering, we can estimate the total time participants would need to commit is 40 hours over a 6-month period.

- initial recruitment assessment 0.5 hours,
- consent signing 0.5 hours,
- baseline survey 1.25 hours,
- final 6-month survey 1 hour,
- anthropometric measurement 1.5 hours (0.25 hours x 6, includes measurement taken at baseline, follow-up, and final assessment).
- 28-Day Behavior Change Practice Program. Hearth Sessions Total 34.5 hours: 12 days per cycle, 2.5 hours per day, for total = 30 hrs. Home-visits during the second half of the program total of 4.5 hours (1.5 hours three time a week for two weeks),
- Health Assessment at the medical facility may take up to 1 hour for medical screening, immunization checks, and collection of baseline height and weight measurements.

If the household participates in three hearth cycles, the time the staff will spend at the family's home is estimated to be 74.5 hours.

For Control arm:

If a household were to complete the full 6-month participation, we can estimate the total time participants would need to commit is 4.75 hours.

- initial recruitment assessment 0.5 hours,
- consent signing 0.5 hours,
- baseline survey 1.25 hours,
- final 6-month survey 1 hour,

- anthropometric measurement 1.5 hours (0.25 hours x 6, includes measurement taken at baseline, follow-up, and final assessment).

Obtaining Consent

On the day of final recruitment, details of the study and the consent process will be explained to mothers. Households will then have one week to reflect on the information provided. During a home visit one week later, and just before the baseline survey, trained staff will obtain informed consent from the mother of the index child. The staff has gone through training to ensure they communicate the following in lay-person language, and in a clear and respectful manner: research time-frame; title of research; researchers involved; purpose of research; description of research; potential harms and benefits; treatment alternatives; statement of confidentiality; information and data to be collected; how long the data will be kept, how it will be stored and who can access it; any conflicts of interest; a statement of the participant's right to withdraw from participation at any point; and a declarative statement of understanding that the potential participant agrees to and signs.

- A copy of the consent form will be provided to the parents of Index child.
- Parents will authorize by signing the consent form that they have read and understand this consent form, and volunteer to participate in this research study.
- For eligible participants with limited literacy, parents will authorize using thumbprint signature that they understand the consent form and volunteer to participate in this research study.

Informed Consent from the Treatment Arm households will be obtained 1 week after communicating the study information with the participants, and 1-2 weeks prior to the 28-Day Behavior Change Practice sessions, and before participants participate in the baseline survey.

Informed Consent from the Control Arm households will be obtained 1 week after communicating the study information with the participant, and before participants in the baseline survey.
